4. STUDY POPULATION

4.1 Population (base)

The study population comprises advanced abdominal cancer patients with gynecological malignancies or tumors in the colon. All patients scheduled for receiving palliative chemotherapy at the department of medical oncology (E30) at the Radboud University Medical Centre, Nijmegen (UMCN) will be recruited. In total, we expect approximately 200 palliative patients, with gynecological malignancies or tumors in the colon, to be scheduled for palliative chemotherapy at the UMCN annually. Taking a radius of 40 km from the UMCN into account, we expect that 40% will be outside this radius. This means that we expect approximately 120 patients to be able to be included in the study in a year.

Eligible patients will be requested to take part in the study after obtaining permission from the treating physician. This request will then be discussed with the patient, whenever possible in the presence of the caregiver, by the nurse or by one of the researchers. Additionally, the patient will receive a written leaflet with further information. The nurse or one of the researchers will ask the patient whether he/she has read the leaflet, whether the information is clear and whether he/she would like to participate in the study. After that, the informed consent form will be signed by the patient and the researcher will register the patient. Our intention is to consider an inclusion period of up to one and a half year.

4.2 Inclusion criteria

In order to be eligible to participate in the study, the patient must meet all of the following criteria:

- age 18 years or older
- diagnosed with advanced colon or gynecological cancer
- receiving primary or secondary palliative chemotherapy according to a three weekly schedule
- living within a 40 km radius around the Radboud University Nijmegen Medical Centre
- written informed consent

4.3 Exclusion criteria

Patients will be excluded from participation in the study according to any of the following criteria:

- renal insufficiency (MDRD-GFR < 60ml/min and/or proteinuria)*
- dementia or any other condition which makes it impossible to fill out questionnaires correctly
- unable to understand or speak Dutch

- _____ depending on artificial nutrition in the form of Oral Nutritional Supplements, tube feeding or total parenteral nutrition

*proteinuria is defined in case of a protein creatinine ratio > 0.5g/10mmol or an albuminuria > 300mg/day. This is checked by default before the start of chemotherapy by the treating physician to decide whether or not the patient is eligible for receiving chemotherapy.

4.4 Sample size calculation

The sample size calculation is based on the primary outcome of this study: the EORTC-QoL-C30 questionnaire for quality of life. The primary outcome of this study is the difference in quality of life between the 2 groups at the start of the 3rd cycle of chemotherapy. Based on literature, advanced cancer patients with gynecological tumors and tumors of the colon have a mean score of approximately 60 points with a standard deviation of 22 points on the EORTC-QoL-C30 questionnaire. Assuming a difference of 10 points, on a scale of 0-100 points, is a clinically relevant difference in favor of FoodforCare at Home, we estimate that 76 patients are needed in each group in order to obtain a power of 80% (two-tailed t-test, alpha=0.05). Assuming a drop-out rate of 20%, this means a total of 180 patients. In order to improve the power significantly, we will make use of the ANCOVA test [31]. By multiplying the number of patients with $(1-(\rho^2))$ a total of 164 patients will be needed. The correlation between the baseline and follow-up outcome T2 (ρ) is estimated at 0.3.

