5. INVESTIGATIONAL PRODUCT

5.1 Name and description of investigational product(s)

In a period of 1.5 year, 164 patients will be randomized into two groups. The intervention group will receive meals from FoodforCare at Home and the control group will continue their usual diet for 3 weeks. The FoodforCare at Home concept consists of five to six small protein and energy enriched meals that will be delivered twice a week. After an individual intake, the composition of the dishes will be tailored to the needs of the patient in terms of composition, diet, taste, flavor and portion size. Besides the meals, patients in the intervention group will also receive an information leaflet about the importance of protein during treatment and how to reach their protein requirements. The control group has no restrictions to their diet. The dishes are prepared every day by Maison van den Boer.

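### Section 4.4 under-inflates for drop-out: 152 completers at 20% loss need 190 patients, not 180, so 164 randomised give about 77–78% power instead of 80%

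*Combined protocol and SAP*

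**What the plan says.** Section 4.4 bases the sample size on the between-group difference in EORTC quality of life at the start of the third chemotherapy cycle. Its inputs are:

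- Difference: "Assuming a difference of 10 points, on a scale of 0-100 points".
- Spread: "with a standard deviation of 22 points on the EORTC-QoL-C30 questionnaire".
- Test: "two-tailed t-test, alpha=0.05".
- Result: "we estimate that 76 patients are needed in each group", this being the number required "in order to obtain a power of 80" per cent.

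Two adjustments follow. The first is for attrition: "Assuming a drop-out rate of 20%, this means a total of 180 patients". The second multiplies by 1 − ρ², with a correlation of 0.3 between baseline and follow-up, and concludes that "a total of 164 patients will be needed". Section 5.1 takes this over as the trial size: "164 patients will be randomized into two groups".

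Section 6.5 adds that further patients will be included to make up for withdrawals. It gives neither a number nor a trigger.

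**The concern.** The step from 76 per group to 180 in total does not match a 20% loss. With 180 patients, losing 20% leaves 144, fewer than the 152 the calculation has just said are needed. All later figures are built on 180, so the error passes into the 164 patients that section 5.1 commits to randomising.

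Three figures are presented as belonging together: 80% power, 20% drop-out and 164 patients. If they are not compatible, the trial runs with a higher chance of missing a 10-point benefit than the protocol states, and any later report that repeats the power statement will be wrong.

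**Working it through.** **Inputs (all from section 4.4).** Difference 10; SD 22; two-sided alpha 0.05; power 80%; drop-out 20%; ρ = 0.3. Equal allocation is inferred from the equal group sizes.

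**Step 1: size per group (reproduces).**
n = 2 × (1.960 + 0.842)² × 22² / 10² = 75.98, so 76 per group and 152 in total. This is the normal approximation. The exact t-test, which is the test the text names, gives 76.95, so 77 per group and 154 in total.

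**Step 2: drop-out (does not reproduce).**
- Correct inflation: 152 / (1 − 0.20) = 190.
- Common shortcut: 152 × 1.2 = 182.4. This is not 180 either.
- Loss that 180 actually covers: 1 − 152/180 = 15.6%.

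**Step 3: ANCOVA factor.**
1 − 0.3² = 0.91.
- As in the plan: 180 × 0.91 = 163.8, so 164. The final figure therefore follows from 180, and the only fault is in step 2.
- Corrected: 190 × 0.91 = 172.9, so 173, or 174 with equal arms.
- Starting from the exact t-test: 154 / 0.8 × 0.91 = 175.2, so 176 with equal arms.

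The order of steps 2 and 3 does not matter: 152 × 0.91 / 0.8 = 172.9.

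**Step 4: completers.**
- Needed: 152 × 0.91 = 138.3 (normal), or 154 × 0.91 = 140.1 (t).
- Available: 164 × 0.8 = 131.2, or 65.6 per group.

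**Step 5: power.**
The residual SD after baseline adjustment is 22 × √0.91 = 20.99. The t column uses the noncentral t with total completers minus 3 degrees of freedom.

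| Randomised | Completers per group at 20% loss | Power, normal | Power, t |
|---|---|---|---|
| 164 | 65.6 | 77.9% | 77.3% |
| 174 | 69.6 | 80.3% | 79.7% |
| 176 | 70.4 | 80.7% | 80.2% |

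The type II error at 164 is thus 22.1% (normal) or 22.7% (t), against the planned 20%.

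**Step 6: drop-out that 164 can absorb at 80% power.**
- Normal: 1 − 138.32/164 = 15.7%.
- t: 1 − 140.14/164 = 14.5%.

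**The case against.** The arithmetic slip itself cannot be defended; the case on the other side concerns its consequence.

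- **Replacement.** Section 6.5 provides for extra inclusions after withdrawals. If patients were replaced until about 140 had data at the third cycle (70 per group gives 80.5% normal, 79.9% t), the shortfall would vanish. This makes the 77–78% conditional on no replacement beyond 164. But section 6.5 names no evaluable target, and the only total in the plan already contains a drop-out allowance. At 20% loss, 140 completers would also mean 140/0.8 = 175 randomised, so the 164 would still be wrong.
- **Timing of drop-out.** Section 4.4 does not say when the 20% is lost. The primary comparison comes about three weeks after the intervention starts, and follow-up continues for three months beyond it. If part of the 20% falls after the third cycle, power is better: 80.3% (normal) or 79.8% (t) with 15% lost by then, and 82.5% or 82.0% with 10% lost. This is a fair point about what may happen. However, section 4.4 applies the 20% to a calculation defined at the third cycle, so it is the plan's own allowance for that endpoint.
- **Size against input uncertainty.** An SD of 21.4 instead of 22, or ρ of 0.37 instead of 0.30, would restore 80% under the normal approximation. That shows the effect is small. It does not make 180 follow from 152 at 20%.
- **Size of the gap.** From the plan's own 76 per group, the gap is 9 patients, or 10 with equal arms. A gap of 12 arises only if 76 is also replaced by the exact t-test value of 77.

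**Conclusion.** The concern holds. The drop-out step should give 190, the final total should be about 174, and 164 randomised patients deliver 77.9% (normal) or 77.3% (t) power, not 80%. The loss is 2.1 to 2.7 points of power. It is modest, but it affects the number on which the trial size rests.

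The result assumes the plan's own inputs, 20% lost by the third cycle, no replacement beyond 164, and the full precision gain from baseline adjustment at ρ = 0.3. The last assumption is not secure: section 8.2 plans adjustment only for confounders that prove unbalanced at baseline. With no gain from baseline, the same 131 completers would give 74.0% (normal) or 73.4% (t). That is a separate matter and is not needed for this conclusion, but it means there is no slack to absorb the error.

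**What to change.** Correct section 4.4 so that the chain reads 152, then 190 at 20% drop-out, then 172.9 after the factor 0.91, rounded to 174 for equal arms. Then make one statement about the planned 164:

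- power is about 77–78% if 20% are lost by the third cycle; or
- power is 80% provided that drop-out by the third cycle is at most about 15%.

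Section 4.4 should also say at which time point the 20% applies. If section 6.5 is meant to protect power, it should name an evaluable target of about 140 patients with third-cycle data.

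Raising enrolment is not required for the correction and may be hard. Section 4.1 expects about 120 patients a year who can be included, so about 120 × 1.5 = 180 over the inclusion period, and 174 would take 174/180 = 97% of them.

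An optional way to recover most of the loss is to prespecify both pre-intervention scores (before chemotherapy and at the second cycle) as covariates; both are already collected. If all visits are correlated at 0.3, which is an assumption beyond the single correlation the plan gives, R² = 2 × 0.3² / (1 + 0.3) = 0.138 and power at 164 is 80.1% (normal) or 79.5% (t).

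The cost is a change of text: one slightly less favourable power figure, with no extra patients or measurements.

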5. INVESTIGATIONAL PRODUCT

5.1 Name and description of investigational product(s)

In a period of 1.5 year, 164 patients will be randomized into two groups. The intervention group will receive meals from FoodforCare at Home and the control group will continue their usual diet for 3 weeks. The FoodforCare at Home concept consists of five to six small protein and energy enriched meals that will be delivered twice a week. After an individual intake, the composition of the dishes will be tailored to the needs of the patient in terms of composition, diet, taste, flavor and portion size. Besides the meals, patients in the intervention group will also receive an information leaflet about the importance of protein during treatment and how to reach their protein requirements. The control group has no restrictions to their diet. The dishes are prepared every day by Maison van den Boer.

5.2 Summary of findings from clinical studies

The relevance of a good nutritional status in cancer patients undergoing chemotherapy has been described in several studies. Observational studies have shown that low nutritional status is associated with reduced survival and quality of life [12, 32]. Not many trials have been done into the effect of nutritional interventions on advanced cancer patients undergoing chemotherapy. Furthermore, the nutritional intervention mostly consists of Oral Nutritional Supplements (ONS), nutritional counselling or parenteral nutrition.

One trial in patients with gastrointestinal tumours undergoing palliative chemotherapy showed no effect of nutritional advice or nutritional supplements on quality of life. However, this study was small (N=68) and compliance to the supplements was low [33]. Another study from 2009 in advanced colorectal cancer patients undergoing chemotherapy found that supplementation with parenteral nutrition slows weight loss and improves quality of life. Patients in this study reached their energy and protein requirements 95-100% of all times [34].

To our knowledge, there is one other study that used regular foods and drinks as a nutritional intervention. The conclusion was that the products increased protein intake but no improvements in physical performance was seen. However, this study was performed in elderly people at home after hospital admission [35].

5.3 Summary of known and potential risks and benefits

The food products of Maison van den Boer meet the highest standards of nutrition and quality and has therefore, no additional risk compared to usual products. All products will be served according to the regular hygienic and food safety criteria that are valid. Possible serious reactions to the products will be noted as SAE's. There are no additional tests or hospital visits necessary for the patient. Therefore, we do not expect any potential risk.

5.4 Dosages, dosage modifications and method of administration

The composition of the FoodforCare at Home dishes are developed to enable maintenance and if possible improvement of the nutritional status of the patient. Therefore, a number of basic principles are chosen which are described below.

The aim is to stimulate protein intake as much as possible in order to maximize protein synthesis during treatment. Protein intake of at least 1.2 g/kg body weight is recommended for cancer patients [36]. On average, this is equivalent to an intake of 90-95 grams of protein per person per day (assuming an average weight of 75-80 kg). Protein intake of 20-25 grams per meal would ensure optimal postprandial protein synthesis in the muscles [37]. This and other information about the protein content of the FoodforCare products will be spread to the patients in order for them to make decisions that contribute to their protein requirements.

6. METHODS

6.1 Study parameters/endpoints

6.1.1 Main study parameter/endpoint

Quality of life:

The main study parameter is the quality of life of advanced cancer patients using FoodforCare at Home. Quality of life will be evaluated using the EORTC-QoL-C30 at every time point. This is a validated questionnaire for measuring quality of life in palliative patients [38]. The global quality of life and the functional scales will be included as the main items in determining the quality of life of the patients. The symptom scales will be analyzed as secondary endpoint. Questionnaires will be scored according to the procedures specified by the EORTC [39].

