Intervention and procedure: Inclusion will take place at the department of Medical Oncology at the start of palliative chemotherapy. Patients will be randomly assigned to one of two groups before the start of the second cycle of chemotherapy. The intervention group will receive meals from FoodforCare at Home and the control group will continue their regular diet for 3 weeks between the 2nd and 3rd cycle of chemotherapy. The FoodforCare at Home meals will be delivered at the patient's home by research assistants or AYA's. These are Adolescents and Young Adults with cancer who are also trained to perform the measurements.

Main study parameters/endpoints: The main study parameter is quality of life of patients receiving FoodforCare at Home compared with patients receiving their usual diet. This will be evaluated by the EORTC-QLQ-c30 at all time points. The secondary endpoints are patient satisfaction, nutritional status, nutritional intake, performance scale, medication use, symptoms and quality of life of the partner/caregiver.

Nature and extent of the burden and risks associated with participation, benefit and group relatedness: There are no additional tests or hospital tests necessary for the patient. This study will not confer any no additional risks. Food will be delivered within the expiration dates and the meals will be prepared according to the regular hygienic and food safety criteria that are valid. Possible serious reactions to the meals will be noted as SAE's.

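### Section 6.1.1 puts the global quality-of-life scale and the functional scales together in the primary endpoint without a deciding score or success rule, while section 4.4 sizes one test of one unnamed score

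*Combined protocol and SAP*

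**What the plan says.** The combined protocol and SAP describes the primary endpoint in several places.

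- **Section 6.1.1:** "The global quality of life and the functional scales will be included as the main items". The next sentence sorts the remaining scales: "The symptom scales will be analyzed as secondary endpoint". Scoring follows the EORTC procedures by reference.
- **Summary:** the main parameter is quality of life. "This will be evaluated by the EORTC-QLQ-c30 at all time points". No scale is named.
- **Section 4.4:** the calculation rests on "the primary outcome of this study: the EORTC-QoL-C30 questionnaire for quality of life". The quantity compared is "the difference in quality of life between the 2 groups at the start of the 3rd cycle of chemotherapy". Patients are said to "have a mean score of approximately 60 points with a standard deviation of 22 points", and a 10-point difference is to be detected with 80% power ("two-tailed t-test, alpha=0.05"). After allowances for dropout and baseline adjustment, "a total of 164 patients will be needed".
- **Section 8.2:** a mixed model is fitted to quality of life, with no scale, testing order or alpha allocation.
- **Section 8.3:** several secondary outcomes are handled like the primary one. It adds nothing on which score decides.

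**The concern.** Section 6.1.1 ranks the scales: symptom scales are secondary, and the global scale and the functional scales (plural) are primary. Section 4.4 treats the primary outcome as one number with one mean, one SD and one test. The two fit together only if one scale decides or the scales are combined into one score, and the plan states neither.

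The rule that turns the data into a primary conclusion can therefore still be chosen after the results are known. This matters more than usual here because the outcome is self-reported and section 6.3 acknowledges that patients know their group. If the global scale and the functional scales point in different directions, the primary objective has no defined answer.

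**Working it through.** **Inputs from section 4.4:** difference 10, SD 22, two-sided alpha 0.05, power 80%, 76 per group, a stated 180 after dropout, rho 0.3, final total 164.

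**Assumed, because the documents do not give them:** the number of main scales k, and a common correlation r between their test statistics. I use k = 3 as the main case (global plus at least two functional scales) and r from 0.8 to 0. The value r = 0 is an outer bound.

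**Step 1. Reproduce the plan's figure.** n per group = 2 × (1.960 + 0.8416)² × 22² / 10² = 2 × 7.849 × 4.84 = 75.98, so 76. The exact t-test gives 79.5% power at 76 and 80.0% at 77. The last step is 180 × (1 − 0.3²) = 163.8, so 164. The calculation is therefore one comparison of one score at undivided alpha.

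**Step 2. Three readings of section 6.1.1.**

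*(a) Each scale tested at 0.05, any success counts.* For independent scales the chance of at least one false positive is 1 − 0.95³ = 14.3%. For correlated scales it is 1 − ∫[Φ((c − √r·g)/√(1 − r)) − Φ((−c − √r·g)/√(1 − r))]^k φ(g) dg, with c = 1.960. These rates count significance in either direction, so they compare with the nominal two-sided 5%.

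*(b) All scales must succeed.* Alpha holds. Suppose each scale has 80% power and all have the same effect and SD. Joint power is then 0.8³ = 51.2% at r = 0, and otherwise ∫Φ((0.8416 + √r·g)/√(1 − r))^k φ(g) dg.

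| r | (a) false-positive rate, k = 3 | (b) joint power, k = 3 |
|---|---|---|
| 0.8 | 9.8% | 68.7% |
| 0.5 | 12.5% | 61.1% |
| 0.3 | 13.6% | 57.0% |
| 0 | 14.3% | 51.2% |

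More scales make both worse. With six scales, a purely illustrative number, (a) runs from 13.9% at r = 0.8 to 26.5% at r = 0.

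*(c) One composite.* There is one test and no alpha inflation. If SD 22 belongs to each single scale and the composite is their plain mean, its SD is 22 × √((1 + (k − 1)r)/k). For k = 3 this is 16.1 (r = 0.3), 18.0 (r = 0.5) and 20.5 (r = 0.8), each below 22. The planned standardised difference is 10/22 = 0.455. The composite reaches it with a difference of 16.07 × 10/22 = 7.3 points at r = 0.3, or 20.48 × 10/22 = 9.3 points at r = 0.8. Power would fall below plan only if the relevant difference shrank below those values. What is missing here is the definition of the composite and inputs that belong to it.

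**The case against.** **Section 4.4 already implies one primary score.** It does imply one test, and it fixes the time point, so when the primary comparison is made is not in doubt. It does not say which score is compared, and section 6.1.1 lists several.

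**Scoring follows the EORTC procedures.** Nothing in the documents says that these yield one score or that a particular score decides. Section 6.1.1 itself separates global, functional and symptom scales.

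**The sizes are hypothetical.** This is fair. The documents do not state the number of scales, and the six-scale figures should carry no weight in judging the point. Three scales is the fewest the wording allows if the scales are tested separately, and even at r = 0.8 the any-of error rate is about twice the nominal level.

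Two stronger readings are tempting, and the documents do not support either.

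- A reader might infer that the plan commits to an inflated error rate. It does not, because it never says that the scales are tested separately or that any success suffices. A composite is also possible.
- A reader might infer that the trial must be much larger to carry several primary scales. That holds if 80% power is wanted on each scale after a Bonferroni correction, but an any-of rule needs only one success. With 164 randomised, 20% lost (164 × 0.8 / 2 = 65.6 per group), SD 22 × √0.91 = 20.99 and the same effect on every scale, Bonferroni any-of power for three scales is about 77% at r = 0.8 and 90% at r = 0.3. Equal effects favour that rule, but the figures show that no general need for a larger trial follows.

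**Conclusion.** The point stands and should be corrected before analysis: the primary endpoint is not reduced to a single decision, and nothing elsewhere in the plan supplies the missing rule. The consequence depends on which reading is adopted:

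- **Any-of, uncorrected:** about 10% to 14% false positives instead of 5%.
- **All-of:** joint power of about 69% to 51% instead of 80%.
- **Composite:** no alpha inflation and no necessary loss of power, but an undefined score to which SD 22 and the 10-point difference cannot be tied.

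The first two ranges assume three scales and equal correlations from 0.8 to 0. The all-of range also assumes 80% power and the same effect on each scale. That the rule is missing depends on none of these assumptions.

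**What to change.** In sections 4.4, 6.1.1 and 8.2, name the same single primary score. It can be one scale, for example global quality of life, or one composite with its components, weights and handling of a missing component written out. State that it is tested at two-sided 0.05 as the between-group difference at the start of cycle 3. Move the remaining functional scales to the secondary endpoints. Confirm that mean 60, SD 22 and the 10-point difference belong to the named score, and redo the sample size if they do not. If an all-of rule or a corrected any-of rule was really intended, state it and size the trial for it.

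If one scale is named and the section 4.4 inputs fit it, the cost is wording only. The downside is small: a benefit seen only on a functional scale would be a secondary result. A composite would also need its own SD and relevant difference.

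Two neighbouring matters are separate and not settled by this change: how the 20% dropout was carried into the total of 164, and whether the primary analysis is the ANCOVA of section 4.4 or the mixed model of section 8.2.
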